3 STUDY OBJECTIVES

3.1 Primary Objective

The primary objective of the study is to characterize repeat dose pharmacodynamics (PD) of SP-102 (10 mg dexamethasone) administered by epidural injection with respect to hypothalamic-pituitary-adrenal (HPA) suppression using plasma cortisol levels, white blood cell count (WBC), and blood glucose.

3.2 Secondary Objective

The secondary objectives of the study are to:

- Evaluate the safety and tolerability of single and repeat dose SP-102 (10 mg dexamethasone) administered by epidural injection in subjects with lumbosacral radiculopathy.

- Evaluate the analgesic effect on leg pain (as measured by the Numeric Pain Rating Scale [NPRS] in the affected leg) following the index (Treatment [T1]) and repeat (T2) injections.

4 ENDPOINTS

4.1 Pharmacodynamic Endpoints

- Dexamethasone-induced HPA suppression as measured by:
 - Observed total blood cortisol levels, change from baseline cortisol levels, and percent change from baseline cortisol levels
 - Observed glucose levels, change from baseline glucose levels, and percent change from baseline glucose levels
 - Observed white blood cell counts, change from baseline white blood cell counts, and percent change from baseline white blood cell counts
- NPRS (average leg pain and back pain) and BPI-SF
- Change from T1 Day 0 and T2 Day 0 through Day 28 in NPRS (average leg pain and back pain) and BPI-SF over time following the index (T1) and repeat (T2) epidural injections, respectively
- Percent change from T1 Day 0 and T2 Day 0 through Day 28 in NPRS (average leg pain and back pain) and BPI-SF following the index (T1) and repeat (T2) epidural injections, respectively

4.2 Safety Endpoints

- Incidence of treatment-emergent AEs (TEAEs) and serious adverse events (SAEs)
- Change from baseline in clinical laboratory parameters, vital sign measurements, ECG findings, physical examination, general neurological examination findings, and targeted neurological examination parameters following each treatment.

5 SAMPLE SIZE

No formal statistical power calculation was performed for this study; the sample size is based on clinical and practical considerations. Enrollment will continue until 12 subjects have each completed two SP-102 injections (T1 and T2).

6 RANDOMIZATION

This is an open-label study; there is no blinding. All subjects will receive SP-102 for each of the injections.

7 PLANNED ANALYSES

No statistical analysis plan (SAP) prepared in advance of the data can be absolutely definitive and the final clinical study report (CSR) may contain additional tables or statistical tests if warranted by the data obtained. The justification for any such additional analyses will be fully documented in the final CSR.

7.1 Analysis Sets

Subjects excluded from the analysis sets and the reason for their exclusion will be listed in Appendix 16.2.

7.1.1 Screened Population

This consist of subjects who signed the ICF and are assigned a study subject number.

7.1.2 Safety Analysis Population

The Safety Analysis population is defined as all enrolled subjects who receive at least one SP-102 injection.

7.1.3 PD Analysis Population

The PD Analysis population is defined as all enrolled subjects who have a T1 period baseline PD result and at least 1 post-dose PD assessment result without any protocol deviations available in either T1 or T2.

Major protocol violations that impact the PD analysis may lead to exclusion from the PD population.

7.1.4 Complete Analysis Population

The Complete Analysis population is defined as all enrolled subjects who receive only one SP-102 injection who complete T1 – Day 28 plus those subjects who receive two SP-102 injections who complete T2 – Day 28.

7.2 Baseline

Unless otherwise specified, baseline is defined as the last non-missing measurement taken prior to treatments T1 or T2 (reference start date). This includes screening or unscheduled assessments that would have been performed no earlier than 21 days before the reference start date.

In the case where the last non-missing measurement and the reference start date coincide, that measurement will be considered pre-reference, but AEs and medications commencing on the reference start date will be considered post-reference.

For laboratory tests, baseline is defined as the last measurement obtained during screening prior to T1.

For vital signs parameters, an assessment performed on reference start date with time point marked as “pre-dose” will be considered as baseline for the given treatment period.

Baseline ECG is the last measurement prior to the index injection.

For physical exams, baseline is defined as the last assessment prior to T1 on Day 0.

For General and Targeted Neurological Exam baseline for each treatment period is defined as the pre-dose assessment.

For cortisol suppression, glucose, and white blood cell counts, baseline is defined as the last non-missing value obtained prior to T1 or T2, which is T1/T2 Day 1 pre-dose measurement.

For NPRS and BPI-SF, baseline is defined as the last non-missing value obtained prior to T1 or T2, which is T1/T2 Day 0 measurement.

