3.5.4.2 Glucose

A glucose level measures the amount of sugar circulating in the blood. Accurate levels of glucose are measured from blood obtained in a fasting state; therefore, the subject will undergo at least a 10-hour fast prior to this being tested at 8 am; this is not required at Screening. Glucose will be measured at Screening, Visit 3 through Visit 10, and Visit 12 through Visit 19. NOTE: The Screening test result is to be compared to the local laboratory normal range for non-fasted glucose.

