3.5.5.5 Laboratory Parameters

The following clinical laboratory tests are to be performed at Screening, Baseline, T1 – Day 5, T1 – Day 28, T2 – Day 5, and T2 – Day 28 (Visit 19/EOS/ET) unless noted below:

Hematology: Hemoglobin, hematocrit, red blood cell count, WBC count (with differential [lymphocytes, neutrophils, eosinophils, basophils, and monocytes]), and platelet count.

Serum Chemistry: albumin, alkaline phosphatase, AST, ALT, direct bilirubin, total bilirubin, blood urea nitrogen, calcium, chloride, creatine kinase (Screening only), creatinine, gamma-glutamyl transferase, glucose, lactate dehydrogenase, potassium, sodium, and uric acid.

Other tests: HbA1c, HIV, hepatitis B, and hepatitis C at Screening. Coagulation tests at Screening or Baseline: activated PTT, PT, and INR. Coagulation tests may be repeated prior to the index and repeat injection, if deemed necessary by the Investigator.

Urinalysis: Dipstick analysis: color, turbidity, specific gravity, pH, glucose, protein, ketones, urobilinogen, bilirubin, blood nitrate, leukocyte esterase, and microscopic examination when indicated by dipstick results.

Urine drug screen: Includes opiates, barbiturates, benzodiazepines, tricyclic antidepressants, cannabinoids, PCP, cocaine, ecstasy, and amphetamines. A urine drug screen will be obtained at Screening, Baseline, and T1 – Day 28. A urine drug screen may be repeated if deemed necessary by the Investigator.

WOCBP: Serum pregnancy test at Screening. Urine pregnancy test at Baseline and at Visit 11 (T2 – Day 0). A urine pregnancy test may be repeated if deemed necessary by the Investigator.

Laboratory samples will be analyzed by the local laboratory. In the event of an unexplained clinically noteworthy abnormal laboratory test value, the test should be repeated immediately and followed up until it has returned to the normal range and/or an adequate explanation of the abnormality is found.

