5.2.3 Analysis Methods

No formal statistical hypothesis testing will be performed in this study, however descriptive statistics will be presented.

Unless otherwise specified, baseline is defined as the last non-missing measurement taken prior to treatments T1 or T2 (reference start date). This includes screening or unscheduled assessments that would have been performed no earlier than 21 days before the reference start date.

In the case where the last non-missing measurement and the reference start date coincide, that measurement will be considered pre-reference, but AEs and medications commencing on the reference start date will be considered post-reference.

For vital signs parameters, an assessment performed on reference start date with time point marked as “pre-dose” will be considered as baseline.

For cortisol suppression, glucose, and white blood cell counts, baseline is defined as the last non-missing value obtained prior to T1 or T2, which is T1/T2 Day 1 pre-dose measurement.

For NPRS, baseline is defined as the last non-missing value obtained prior to T1 or T2, which is T1/T2 Day 0 measurement.

Details on definition of baseline and calculations for the change and percent change in PD values will be defined in detail in the SAP.

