7.12.2 Laboratory Data

Descriptive statistics of the observed values and change from baseline (continuous data) will be presented by treatment period and visit (Screening, T1 – Day 5, T1 – Day 28, T2 – Day 5, and T2 – Day 28 (Visit 19/EOS/ET)) for each hematology (Hemoglobin, hematocrit, red blood cell count, WBC count (with differential [lymphocytes, neutrophils, eosinophils, basophils, and monocytes]), and platelet count), serum chemistry (albumin, alkaline phosphatase, AST, ALT, direct bilirubin, total bilirubin, blood urea nitrogen, calcium, chloride, creatine kinase (Screening only), creatinine, gamma-glutamyl transferase, glucose, lactate dehydrogenase, potassium, sodium, and uric acid), and urinalysis (Dipstick analysis: color, turbidity, specific gravity, pH, glucose, protein, ketones, urobilinogen, bilirubin, blood nitrate, leukocyte esterase, and microscopic examination when

indicated by dipstick results) parameter. Each measurement (continuous data) will be classed as below, within, or above normal range, based on ranges supplied by the laboratory used. Shift tables in relation to the normal range from baseline to each follow-up visit will be presented.

The following lab parameters will be listed only. HbA1c, HIV, hepatitis B, and hepatitis C at Screening. Coagulation tests at Screening or Baseline: activated PTT, PT, INR, serum pregnancy test at Screening, urine pregnancy test at Baseline and at Visit 11 (T2 – Day 0), and MRI.

A listing of any clinically significant laboratory measurements recorded throughout the study will be presented.

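### The SAP takes the safety-laboratory baseline from Screening before T1 for both periods, so T2 laboratory changes start from a value about 4 to 11 weeks old; which baseline rule governs safety glucose and WBC is left open

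*SAP*

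**What the plan says.** **Protocol.** Section 3.5.5.5 schedules the safety panel twice before T1: "The following clinical laboratory tests are to be performed at Screening, Baseline", followed by Day 5 and Day 28 of each period. Section 5.2.3 gives the general rule, "baseline is defined as the last non-missing measurement taken prior to treatments T1 or T2 (reference start date"), with a 21-day look-back and no separate rule for safety laboratory tests. Section 5.2.8 states the laboratory safety endpoint as change from baseline following each treatment.

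**SAP.** Section 7.2 repeats the general rule and its limit ("performed no earlier than 21 days before the reference start date"), then makes an exception: "For laboratory tests, baseline is defined as the last measurement obtained during screening prior to T1". Section 7.12.2 is consistent with that exception. It says "change from baseline (continuous data) will be presented by treatment period and visit (Screening", then names T1 Day 5, T1 Day 28, T2 Day 5 and T2 Day 28. The Baseline visit is not listed.

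**Glucose and WBC.** SAP 7.2 also says: "For cortisol suppression, glucose, and white blood cell counts, baseline is defined as the last non-missing value obtained prior to T1 or T2", which it identifies as the Day 1 pre-dose sample of each period. Both analytes are also in the 7.12.2 safety panels. Protocol 3.5.4.2 asks for a 10-hour fast before glucose sampling but waives it at Screening, and adds: "The Screening test result is to be compared to the local laboratory normal range for non-fasted glucose".

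**The concern.** Two separate problems follow from the laboratory sentence in SAP 7.2.

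First, the SAP departs from the protocol's per-injection baseline and leaves a later scheduled pre-T1 panel unused. A T2 change measured from a pre-T1 value cannot be read as a change following T2. It also contains whatever the first injection did and any drift between injections. SAP 7.2 gives vital signs and neurological examinations a baseline for each period, so laboratory tests are treated differently without a stated reason.

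Second, two rules in the same section cover glucose and WBC and give different baselines. If the laboratory rule is used in the safety tables, the glucose change column may set a non-fasted start against fasted follow-up, and one report would carry two baselines for the same analyte.

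**Working it through.** **Inputs**
- Screening window: Day -21 to Day -1 (protocol 3.5.2.2).
- T1 to T2 interval: 4 to 8 weeks, or 28 to 56 days (protocol 3.4.2).
- Follow-up: 28 days after each injection (protocol 3.1); Day 28 visits have a ±2-day window.
- Maximum participation: 15 weeks (protocol 3.2).
- Day numbering: the SAP has no Day 0 (7.2.1), so Day -21 is 21 days before injection. The protocol has a Day 0 before the Day 1 injection, so Day -21 is 22 days before.

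**Check on the timing inputs.** 21 + 56 + 28 = 105 days = 15.0 weeks, which reproduces the protocol's figure.

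**Age of the Screening value.** Age at T2 = days from Screening to T1 + days from T1 to T2. T2 Day 28 is 27 days after injection on Day 1.

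| | SAP numbering | Protocol numbering |
|---|---|---|
| Shortest, at T2 | 1 + 28 = 29 d (4.1 wk) | 2 + 28 = 30 d (4.3 wk) |
| Longest, at T2 | 21 + 56 = 77 d (11.0 wk) | 22 + 56 = 78 d (11.1 wk) |
| Longest, at T2 Day 28 | 77 + 27 = 104 d | 78 + 27 = 105 d |

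Even the shortest case, 29 days, is longer than the 21 days allowed by the SAP's general rule.

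**Age under a per-injection rule.** For T1, the Day 0 panel is 1 day before injection. For T2, the last panel shown in the readable text is T1 Day 28, and its age at T2 is the interval minus 27 days:
- 28-day interval: 28 − 27 = 1 day.
- 48-day interval: 48 − 27 = 21 days.
- 56-day interval: 56 − 27 = 29 days (27 to 31 with the visit window).

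The T2 baseline would then be about 1 to 29 days old instead of 29 to 78. Beyond a 48-day interval, a T1 Day 28 panel drawn on its nominal day would breach the 21-day limit unless it is exempted.

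**Glucose, visit by visit.** Protocol 3.5.4.2 lists glucose at Screening, Visits 3 to 10 and Visits 12 to 19, fasted except at Screening.
- The panel's follow-up visits are Visits 7 and 10 (T1 Day 5, Day 28) and 16 and 19 (T2 Day 5, Day 28). All fall under the fasting requirement.
- The Day 1 pre-dose samples (Visits 3 and 12) are fasted.
- Visit 2 (T1 Day 0) is not listed, so the Baseline panel is not documented as fasted.

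A fasting mismatch therefore arises only in the 7.12.2 tables, and only if the laboratory rule governs glucose there.

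**The case against.** **The glucose problem may not exist.** A reader might infer that the study will measure the glucose effect from a non-fasted start. The documents do not support that. The Day 1 pre-dose rule names glucose and WBC and is not confined to PD tables. The PD summaries, AUEC28 and Emax use it, and that sample is fasted. Screening glucose is only excused from fasting, so it is not necessarily non-fasted. Nor would the Day 0 panel cure a mismatch, since it is not documented as fasted. All of this stands. What remains is an unresolved choice between two rules in the safety tables. The 7.12.2 visit list, whose only pre-dose visit is Screening, leans towards the laboratory rule.

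**Shift tables are partly protected.** The protocol reads Screening glucose against a non-fasted range, so each value can be classified on its own range. This stands, and leaves the change-from-baseline column as the main exposure.

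**A single pre-index baseline is legitimate.** It shows cumulative change, the SAP uses one for ECG and physical examination, and T1 Day 28 observed values appear in the same tables. The protocol's rule begins with an allowance for exceptions, and section 5.2 lets the SAP carry deviations. This supports keeping the cumulative view. It does not supply a change following T2, and the readable text of SAP Section 10 does not declare the departure.

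**The phrase about screening may mean any time before T1.** Possible, but Screening is a named visit and 7.12.2 omits Baseline.

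**Redaction.** The schedule tables and visit procedures are blacked out, so a T2 Day 0 panel cannot be excluded. This stands, and the fix must allow for it.

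**Conclusion.** The point holds for descriptive safety-laboratory tables. As written, the SAP leaves the scheduled Baseline panel unused and measures T2 laboratory changes from a value 29 to 78 days before T2, and up to 104 to 105 days before T2 Day 28. Those changes do not isolate the second injection, which is what the stated safety endpoint asks for.

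For glucose and WBC the finding is an ambiguity: two rules conflict and the SAP does not say which applies in 7.12.2. It would be tempting to conclude that a steroid-induced glucose rise will be hidden from the study. That goes too far, because the PD analyses and the primary objective rest on the Day 1 pre-dose baseline.

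The conclusion assumes that screening in SAP 7.2 means the Screening visit and that Baseline in protocol 3.5.5.5 means T1 Day 0. The latter is suggested by the same section listing the pregnancy test at Baseline and, separately, at T2 Day 0. It should be corrected before the SAP is signed.

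**What to change.** 1. Replace the laboratory sentence in SAP 7.2 with: *For laboratory tests, T1 baseline is the last non-missing value before the T1 injection; for glucose and WBC, in safety as well as PD tables, baseline is the T1/T2 Day 1 pre-dose value.*
2. For the T2 period, show change from the last non-missing panel before the T2 injection beside the cumulative change from the pre-T1 baseline. That panel is T2 Day 0 if one is scheduled, otherwise T1 Day 28. State that the 21-day limit does not apply to it.
3. Add the pre-dose baseline visit to the 7.12.2 visit list.
4. If any part of the Screening rule is kept, record the departure from protocol 5.2.3 in SAP Section 10.

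The cost is SAP wording, one visit entry and one extra T2 column. On the readable protocol text (3.5.4.2, 3.5.4.3 and 3.5.5.5) the samples are already scheduled; the redacted schedule should be checked for a T2 Day 0 panel.

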3.5.5 Safety Assessments

3.5.5.1 Physical Examination

A complete physical examination, including examination of general appearance, skin, neck, eyes, ears, nose, throat, heart, lungs, abdomen, lymph nodes, extremities, and musculoskeletal system, will be performed at Screening. The Screening physical examination will also include an assessment of lumbosacral radiculopathy. Specific musculoskeletal examination focusing on lumbar spine and lower extremities to exclude musculoskeletal sources of the predominant pain, such as SI joints and trigger points, will be performed in standardized manner and recorded. A physical examination will be done at Screening, T1 – Day 0, T1 – Day 28, and T2 – Day 28 (Visit 19/EOS/ET).

3.5.5.2 General Neurological and Targeted Neurological Examinations:

A general neurological examination will include evaluation of mental status (awareness of person, place, and time), cranial nerves, motor function and balance, sensory exam (ability to feel), and reflexes. A targeted neurological examination focusing on signs and symptoms of lumbosacral radiculopathy, including straight leg raise test, will be performed according to the checklist (see [Appendix G](#)). Both general and targeted neurological exams are to be performed by the same trained clinician throughout the study, if possible. Training for conducting examination will be available on video. General and targeted neurological examinations will be performed pre-dose and post dose on T1 – Day 1, pre-dose and post dose on T2 – Day 1, and on T2 – Day 28 (Visit 19/EOS/ET).

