5.2.8 Safety Analyses

Safety endpoints are as follows:

- Incidence of treatment-emergent adverse events (TEAEs) and SAEs
- Change from baseline in clinical laboratory parameters, vital sign measurements, ECG findings, physical examination, general neurological examination findings, and targeted neurological examination findings following each treatment

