7.2.5 Unscheduled Visits

Except for ET assessments, only scheduled post-baseline laboratory and vital signs values will be tabulated. Post-baseline repeat/unscheduled assessments will be disregarded, although these post-baseline assessments will be listed in the relevant appendices to the CSR.

For post-baseline PD, laboratory and vital sign data, if an Early Termination assessment falls between two visits and the visit prior to that ET visit has a valid assessment, then that ET assessment will be mapped to the subsequent visit within the treatment period. If the scheduled assessment prior to an ET assessment is missing, then the ET assessment will be mapped to that prior assessment. Assessments from T1 cannot be assigned to T2.

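### In subjects given both injections, the neurological exam analysis sees only same-day change after T1; a later change still present at T2 pre-dose is absorbed into the T2 baseline

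*SAP*

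**What the plan says.** - **Endpoint.** Protocol 5.2.8 lists change from baseline in general and "targeted neurological examination findings following each treatment"; SAP 4.2 has "general neurological examination findings, and targeted neurological examination parameters following each treatment". The secondary objective covers both single and repeat dosing. The protocol synopsis says shifts in neurological findings will be summarized by treatment group.
- **Schedule.** Protocol 3.5.5.2 has both neurological exams "performed pre-dose and post dose on T1 – Day 1, pre-dose and post dose on T2 – Day 1, and on T2 – Day 28", the last being Visit 19/EOS/ET. SAP 7.12.6 gives the same five exams and says only that results will be summarized and listed.
- **Baseline.** SAP 7.2: "For General and Targeted Neurological Exam baseline for each treatment period is defined as the pre-dose assessment".
- **Contrast with the physical exam.** SAP 7.2: "For physical exams, baseline is defined as the last assessment prior to T1 on Day 0". Protocol 3.5.5: "A physical examination will be done at Screening, T1 – Day 0, T1 – Day 28, and T2 – Day 28 (Visit 19/EOS/ET"). It therefore has a T1 Day 28 assessment and a baseline that is not reset at T2.
- **Adverse events.** SAP 7.12.1 assigns a treatment-emergent event to the last injection given before it began. The same section also places events starting at Visit 3 or later but before Visit 11 in T1, and events starting at Visit 11 or later in T2.
- **Subjects without T2.** Protocol 3.5.3 sends them to the Visit 19/EOS/ET procedures.

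**The concern.** The endpoint asks for neurological change after each injection, but in two-injection subjects the two periods are not observed alike. T1 is examined on the injection day and then not again until just before T2. The SAP uses that exam only as the starting point for T2. A reflex, sensory or straight-leg-raise change that emerges in between has no place in the T1 change from baseline and cancels out of the T2 change.

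Protocol 1.1.2 and 1.8 present serious neurologic events as the main safety concern with epidural corticosteroids. A T1 table built this way could be read as showing no delayed neurological change after a first injection, when it shows that none was looked for after the first day.

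**Working it through.** The plan states no figure for this endpoint, so there is none to reproduce. The check lays the exam schedule against the baseline rule.

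**Step 1. Role of each exam in a two-injection subject** (schedule from Protocol 3.5.5.2 and SAP 7.12.6; baseline from SAP 7.2; interval from Protocol 3.1).

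| Exam | Timing | Role in the planned analysis |
|---|---|---|
| T1 Day 1 pre-dose | before T1 | T1 baseline |
| T1 Day 1 post-dose | same day as T1 | T1 change |
| T2 Day 1 pre-dose | 4 × 7 = 28 to 8 × 7 = 56 days after T1 | T2 baseline only |
| T2 Day 1 post-dose | same day as T2 | T2 change |
| T2 Day 28 (Visit 19) | end of T2 follow-up | T2 change |

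Counting exams that enter as change: T1 has one same-day and no late exam; T2 has one same-day and one late exam.

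**Step 2. Follow one sign through the rule.** Score it 0 if absent and 1 if present. Suppose it appears after T1 Day 1 and persists. The five exams read 0, 0, 1, 1, 1.

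- T1 change: 0 − 0 = 0.
- T2 change, post-dose and Day 28: 1 − 1 = 0.
- If the sign has gone by T2 Day 28, the T2 change is 0 − 1 = −1, an apparent improvement after T2.
- The contrast that is not planned, T2 pre-dose against T1 pre-dose: 1 − 0 = +1. This is the only one that shows the sign arising after T1.

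**Step 3. The adverse event route.** Visit 11 is the T2 baseline visit (Day 0); Visit 12 is T2 Day 1, where the pre-dose exam takes place. Take a sign first found, and dated, at Visit 11 or at Visit 12 before dosing.

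- By the last-injection rule it belongs to T1, because T2 has not been given.
- By the visit rule it belongs to T2.
- SAP 7.2 also treats adverse events starting on the dosing date as post-reference, which for Visit 12 points to T2 as well.

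The rules conflict for exactly the events that the T2 pre-dose exam would uncover.

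**Step 4. Subjects without T2.** They have the T1 same-day exam and, if they attend, the Visit 19/EOS/ET exam. With no T2 pre-dose exam, the only available baseline is T1 pre-dose. Both documents label that visit as T2 Day 28, and no sentence says how its neurological result is tabulated for these subjects.

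**Step 5. Size.** Enrollment runs until 12 subjects have had both injections. Late T1 exams counted as T1 change are 0 of 12 as written, and up to 12 of 12 if the T2 pre-dose exam is also used. For scale only:

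- With no finding in 12, the one-sided 95% upper bound is 1 − 0.05^(1/12) = 22.1%.
- The chance of at least one finding is 1 − (1 − p)^12: 46% for p = 5%, 72% for p = 10%, 93% for p = 20%. These rates are assumptions; the documents give none.

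**The case against.** The strongest reply is that this is a small descriptive study, that period-specific baselines are a normal way to describe change after each injection, and that a new sign would be caught elsewhere. Much of that stands, and it rules out several stronger readings that a reader might infer.

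- **That delayed findings belong to no treatment, or that single-dose neurological safety cannot be assessed.** Not supported. The gap is in the exam change-from-baseline analysis of two-injection subjects. Treatment-emergent events are assigned to a treatment, the same-day T1 exam is available, subjects without T2 have a Visit 19 exam, and all results are listed, so the missing contrast can be rebuilt by hand.
- **That exam-only changes never become adverse events.** Not supported. Protocol 4.1.1 counts any unfavorable sign, and 3.4.8.1 requires illnesses first detected or worsening during the study to be recorded. Under-reporting is possible but is not built into the plan.
- **That the plan tabulates the Visit 19 exam of a T1-only subject under T2.** Nothing directs this. SAP 7.2.5 says "Assessments from T1 cannot be assigned to T2", although its paragraph opens with PD, laboratory and vital-sign data. The handling is unstated rather than wrong.
- **That a formal T1-versus-T2 neurological comparison is biased.** None is planned; the summaries are descriptive.
- **That physical exam and ECG share the defect.** They do not: both have a T1 Day 28 assessment and a baseline before T1.

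Two further points stand. An adverse event of special interest bars a repeat injection (Protocol 3.3.3), so some serious deficits would never reach a T2 baseline; the list is redacted, so how many cannot be judged. And T2 is given only when a repeat injection is judged warranted, while the targeted exam measures signs of the radiculopathy itself. A shift from T1 pre-dose to T2 pre-dose therefore mixes returning disease with any injection effect.

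None of this removes the core point. Listings are not a planned contrast. The late exams in T1-only subjects come from a selected group and do not fill the gap for the others. The adverse event route has the conflict shown in Step 3.

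**Conclusion.** The point holds in limited form. In subjects who receive both injections, the exam analysis covers T1 on the injection day only and T2 to Day 28. A change that develops in the 28 to 56 days after T1 and persists to T2 pre-dose is absorbed into the T2 baseline, and is credited to T1 only through adverse event reporting or by reading the listings. This affects the exam tables of all 12 planned two-injection subjects. It does not leave single-dose neurological safety unassessed, and it does not touch the PD analysis.

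The conclusion assumes that the five-exam schedule is complete. The schedule tables and visit procedures are redacted, but the two readable statements of the schedule agree. It is a cheap improvement worth making before the SAP is finalized.

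**What to change.** In SAP 7.2 and 7.12.6:

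1. Keep the T2 Day 1 pre-dose exam as the T2 baseline, and also tabulate it as late T1 follow-up, as a shift from the T1 Day 1 pre-dose exam.
2. For subjects who do not receive T2, tabulate the Visit 19/EOS/ET exam as T1 follow-up, as a shift from T1 pre-dose.
3. Show T2 post-dose and Day 28 shifts from T1 pre-dose next to those from T2 pre-dose.

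In SAP 7.12.1, reconcile the two attribution rules so that an event dated at Visit 11, or at Visit 12 before dosing, has one stated treatment period.

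No change is needed for physical exam or ECG data.

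The cost is SAP wording and one or two extra descriptive tables, with no new visits or procedures. The tables need a footnote: shifts in targeted-exam items such as straight leg raise also reflect the course of the radiculopathy in subjects judged to need a repeat injection, so they should not be read as injection effects alone.
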